#### 7.2.4 Treatment Start and End

Treatment start is defined as the first day of administration of study drug (Day 1) for Parts 1 & 2 of the study. For Part 3, Treatment start is defined as Day 1 of treatment period 1.

In Part 1 of the study, treatment is received as a single dose therefore treatment end is also Day 1.

For Part 2, treatment end is defined as the final day of administration of study drug which is scheduled as Day 10.

In Part 3, treatment is received as a single dose within the treatment period therefore treatment end is Day 1 of treatment period 2.

#### 7.2.5 Planned dose and actual dose received

Planned dose of study drug depends on the cohort to which the subject was enrolled and will be determined by the SAC. Actual dose received is defined as the actual dose of study drug received regardless of enrolled cohort and is recorded on the electronic Case Report Form (eCRF).

#### 7.2.6 Incomplete Dates

For calculation purposes, incomplete dates will be completed using worst-case, the most conservative value possible. For example, if the start date has a missing day value, the first day of the month will be imputed for study day computations. If day is missing for an end date, the last day of the month will be imputed. Similar logic will be assumed for missing month and year components.

#### 7.2.7 Non-Numeric Values Recorded in Numeric Fields

In the case where a variable is recorded as ">x", " $\ge$ x", "<x" or " $\le$ x" rather than an exact number, then for analysis purposes a value of x will be taken. Where a range of values is quoted the midpoint of the range will be taken.

## 7.3 Missing Data and Withdrawals

In general, data will not be imputed. Where imputation may be deemed appropriate, information is detailed in the analysis descriptions.

## 7.4 Analysis Sets

The **Screened Set** includes all subjects screened for the study irrespective if they were enrolled into the study.

The **Enrolled Set** includes all subjects who passed screening irrespective of whether they received the study treatment.

The **Safety Analysis Set (SAF**) will consist of all subjects who receive at least one dose of study treatment. Subjects will be analysed according to the treatment actually taken.

The **PK Concentration Set** will consist of those subjects in the SAF who have at least one quantifiable serum PK concentration recorded. Subjects will be analysed according to the treatment actually taken.

The **PK Parameter Set** will consist of those subjects in the SAF with sufficient concentration time data to determine at least one quantifiable serum PK parameter. Subjects will be analysed according to the treatment actually taken.

The **PK Sputum Concentration Set** will consist of those subjects for Parts 2 & 3 in the SAF who have at least one quantifiable induced sputum PK concentration recorded. Subjects will be analysed according to the treatment actually taken.

All protocol deviations will be assessed by Zambon and documented on a case-bycase basis prior to the database lock, and important deviations considered having a serious impact on the PK analysis will lead to the relevant subject being excluded from the relevant sets.

The definitions for the analysis sets are sufficient to determine the subjects included within these analysis sets and so do not require listing and agreeing prior to database lock.

For Part 3 of the study, planned study treatment sequence will be determined from the randomisation list. Actual treatment received will be derived by reconciling the kit number entered in to the CRF with the kit list supplied by Zambon.

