9.3. Populations for Analyses

Safety Analysis Set (SAF) will consist of all subjects who receive at least one dose of IMP. Subjects will be analysed according to the treatment actually taken.

The Pharmacokinetic (PK) Concentration Set will consist of those subjects in the SAF who have at least one serum PK concentration recorded. Subjects will be analysed according to the treatment actually taken.

The PK Parameter Set will consist of those subjects in the SAF with sufficient concentration-time data to determine at least one serum PK parameter. Subjects will be analysed according to the treatment actually taken.

The PK Sputum Concentration Set will consist of those subjects in the SAF who have at least one induced sputum PK concentration recorded. Subjects will be analysed according to the treatment actually taken.

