# **Modification History**

Version	Change History	Reason	Date 12AUG2020
1.0	First Version	N/A	
2.0	
 
Update to protocol deviations listing to only important PDs
 
Removed exposure table from analysis
 
Updated AESI to tabulate if necessary
 
Added Sputum plug and processed sputum to analysis
 
	
 
To bring in line with SQN current processes
 
Following client review of dry run TFL
 
	280CT2020

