## 2 CHANGES FROM THE PROTOCOL PLANNED ANALYSIS

For the PK analysis, linearity ratios will not be reported due to the likelihood that  $AUC_{0-}$  inf cannot be obtained.

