- If all the values are BLQ, then the arithmetic mean, arithmetic standard deviation (SD), median, min and max will be presented as zero, and the geometric mean and geometric coefficient of variation (CV) will be denoted as NC (not calculable).

The PK parameters will be listed together with the sample collection details for each study Part.

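### The SAP limits the PK Concentration and Sputum Concentration Sets to subjects with a quantifiable value; the protocol does not, and the change is undeclared

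*SAP*

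**What the plan says.** **Serum set.** Protocol 9.3 includes members of the Safety Analysis Set who "have at least one serum PK concentration recorded". SAP 7.4 requires "at least one quantifiable serum PK concentration recorded".

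**Sputum set.** Protocol 9.3 includes those who "have at least one induced sputum PK concentration recorded". SAP 7.4 requires "at least one quantifiable induced sputum PK concentration recorded".

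**Parameter set.** SAP 7.4 adds the same adjective here: enough data "to determine at least one quantifiable serum PK parameter".

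**Declared changes.** SAP section 2 declares one departure from the protocol analysis: "linearity ratios will not be reported due to the likelihood that" AUC0-inf will be unobtainable. The Modification History gives four items for version 2.0, such as "Added Sputum plug and processed sputum to analysis". None concerns the analysis sets.

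**BLQ handling.** SAP 7.12.1 sets serum BLQ values before the first quantifiable one to zero and treats later ones as missing. In the serum summaries, BLQ values not already made missing count as zero. It adds: "If all the values are BLQ, then the arithmetic mean, arithmetic standard deviation (SD), median, min and max will be presented as zero". SAP 7.12.2 gives no BLQ rule for sputum and makes the sputum summaries optional.

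**Where the sets are used.** Under SAP 7.5.3 the PK sets govern the PK listings as well as the summaries. Under SAP 7.6, membership of the PK sets is counted and the reasons for leaving a subject out of each set are listed.

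**The concern.** A BLQ result from a dosed and properly sampled subject is a valid observation: the concentration lay below the assay limit. Once membership requires a quantifiable value, it depends on the outcome, and the subjects removed are those with the lowest exposure.

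The study's PK objectives are to characterise systemic exposure after inhalation, and the protocol's benefit/risk section expects that exposure to be low. The concentration set is also the natural place for such subjects to appear, because a zero Cmax or AUC cannot enter a log-scale model. Under SAP 7.4 their results would appear in no PK table or PK listing.

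The wording carries weight because SAP 7.4 treats the definitions as sufficient in themselves, with no agreed list of members needed before database lock. A reader comparing the two documents would not learn of the change from the section meant to declare it.

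**Working it through.** The plan gives no figure that depends on these definitions, so there is nothing of its own to reproduce. The check has three steps.

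**1. Who is removed.** The SAP sets are defined per subject and name no analyte or period. A subject leaves the serum set only if every serum sample is BLQ for both voriconazole and N-oxide voriconazole.
- In Part 3 each subject also takes 200 mg oral voriconazole. One quantifiable serum value after that dose keeps the subject in, even if every ZP-059 sample is BLQ.
- The serum effect therefore falls mainly on Parts 1 and 2, and most plausibly on low doses. The lowest fixed dose is 5 mg in SAD cohort 1.

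**2. Effect on a serum mean, if it happens.** Inputs: cohorts of 6 (SAP 3.3), a minimum of 4 evaluable subjects (SAP section 4), and BLQ = 0 for summaries (SAP 7.12.1).

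Let n subjects contribute at a time point, k of them all-BLQ, and let S be the sum over the other n-k. Keeping everyone gives S/n. The SAP set gives S/(n-k). The ratio is n/(n-k), wherever S is above zero.

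| n | k = 1 | k = 2 | k = 3 |
|---|---|---|---|
| 6 | 6/5 = 1.20 | 6/4 = 1.50 | 6/3 = 2.00 |
| 4 | 4/3 = 1.33 | 4/2 = 2.00 | 4/1 = 4.00 |

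With k = 0 the ratio is 1.00. The shift is never downward.

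**3. How often it might happen.** The documents give no limit of quantification and no expected concentration, so this step rests on assumption. If each subject independently has probability p of being all-BLQ, the chance of at least one in a cohort of 6 is 1 - (1-p)^6:

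| p | At least one of 6 |
|---|---|
| 0.01 | 5.9% |
| 0.05 | 26.5% |
| 0.10 | 46.9% |
| 0.20 | 73.8% |

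To tie p to an assay limit, assume a log-normal peak at the sampled times with geometric mean r times the limit. Then p = Φ(-ln r / σ), with σ = √ln(1 + CV²).
- r = 2: p = 0.036 at CV 40% and 0.2025 at CV 100%. The chance of at least one in 6 is 19.7% and 74.3%.
- r = 5: p is about 0 at CV 40% and 0.0266 at CV 100%. The chance is about 0% and 14.9%.

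The outcome ranges from negligible to likely, depending on a number the documents do not contain.

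**Sputum.** The same ratio cannot be carried over. The BLQ-as-zero rule covers serum only, and the general rule in SAP 7.2.7 takes a value recorded as less than x to be x, so zero is not an established comparator. Nor is 6 the denominator: it is the Part 3 screening minimum for sputum producers, and all 16 subjects attempt samples.

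**The case against.** The strongest reply is that this is a wording difference with little consequence, and much of that reply stands.

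- **The formal analyses do not change.** The power model and the geometric mean ratios use log Cmax and log AUC. An all-BLQ subject cannot enter them under either definition. This stands: the effect is confined to descriptive concentration summaries and listings.
- **The exclusion is visible.** Set counts and exclusion reasons are reported under SAP 7.6. A reader might infer that the rule hides low exposure, but the documents do not support that. What is lost is the subject's own results.
- **The BLQ rules do not contradict 7.4.** A reader might infer that they do. The rule for leading BLQ values presupposes a later quantifiable one, and the all-BLQ rule can be read as covering a summary cell, such as a pre-dose time point across subjects. The rules can be applied together with 7.4. They show only that a retained all-BLQ subject would count as zero.
- **Any bias runs against a low-exposure claim.** It would overstate inhaled exposure, and the protocol plans no hypothesis test. This is fair, but an overstated mean still misdescribes systemic PK.
- **The protocol's condition of a recorded concentration might already exclude BLQ.** In that case the SAP clarifies an ambiguity. The protocol does not say so, and a clarification that decides membership still belongs in section 2.

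None of this removes the two facts that remain: the condition is new and undeclared, and it selects on the outcome.

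**Conclusion.** The point holds in limited form. SAP 7.4 adds an outcome-dependent condition to two sets that Protocol 9.3 defines without it, and SAP section 2 does not declare this. If all-BLQ subjects occur, the descriptive serum mean in a cohort of 6 is multiplied by 1.20, 1.50 or 2.00 for 1, 2 or 3 of them. These factors assume that BLQ counts as zero, as SAP 7.12.1 provides for serum, and that all 6 contribute at the time point.

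A reader might conclude that low-dose means will be inflated. The documents do not support that: with no assay limit or expected concentration given, it cannot be known whether any subject will be all-BLQ, and with none the effect is zero. For sputum, the set is narrowed but no size of effect is established. The relative-bioavailability and dose-proportionality estimates are not affected.

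**What to change.** 1. In SAP 7.4, restore the protocol definition for the PK Concentration Set and the PK Sputum Concentration Set. Specify at least one post-dose result recorded, with BLQ counted as recorded. The post-dose condition matters because otherwise a single pre-dose BLQ sample would qualify a subject.
2. Report the number of all-BLQ subjects by dose (Parts 1 and 2) and by treatment (Part 3). Counting by treatment also shows Part 3 subjects who are all-BLQ after ZP-059 but stay in the set through the oral period.
3. State a BLQ rule for the sputum summaries in SAP 7.12.2.
4. Keep the quantifiability requirement in the PK Parameter Set only.
5. If the sponsor prefers the restriction, declare and justify it in SAP section 2.

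The cost is a few words in two definitions, one sentence on sputum BLQ and one count per table. No additional data are needed. If no subject is all-BLQ, the serum results are the same under either wording.

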## 7.5 Data presentations

#### 7.5.1 Parts 1 & 2 Specific Presentations

For each study part, safety and PK data will be summarised by ZP-059 dose only and all other data will be summarised in tabular form by ZP-059 dose group and overall.

Listings will be sorted by study part, ZP-059 dose group, screening number and date/time of assessment.

Dose groups will be presented in the following order using these labels:

- ZP-059 5mg
- ZP-059 XXmg, etc.

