Dose levels for Part 2 will be determined from review of safety data from Part 1.

Details of ZP-059 (investigational medicinal product) are provided in the Investigational Medicinal Products section of this synopsis.

In each cohort, subjects will receive inhaled doses either once daily (QD) for 10 days or twice daily (BID) for 9 days and once in the morning of Day 10, as determined by the Sponsor based on data obtained in previous Part 1. In the event of QD dosing subjects will receive QD doses of ZP-059 (at Hour 0) on Days 1 to 10. In the event of BID dosing, ZP-059 will be administered at Hours 0 and 12 on Days 1 to 9 and once in the morning of Day 10 (i.e. 19 doses in total). Subjects will be required to fast (water permitted) for at least 1 hour prior to each dose and 1 hour post each dose; in the event of BID dosing this will be for both the 0 hour and the 12 hour doses. Following the first dose, subsequent doses will be administered within +/- 1 hour of the scheduled dosing time. If any of the additional cohorts (i.e. Cohorts 4 and 5) are required, subjects will receive either QD or BID doses, as may be appropriate.

For the first 2 subjects in each cohort, there will be a minimum interval of 20 minutes between dosing (Day 1; Hour 0). After the second subject is dosed there will be at least a 30 minutes observation period before the remaining 4 subjects are dosed (Day 1; Hour 0). The remaining subjects will be dosed if the first two subjects show

no clinically significant safety or tolerability concerns (including vital signs measurements, spirometry, physical examinations (symptom directed if required) and review of any adverse events [AEs] including any acute side effects e.g. excessive coughing) at the discretion of the investigator. Any clinically significant findings from the first two subjects in the opinion of the investigator will be discussed with the Sponsor prior to dosing of the remaining 4 subjects. The dosing interval between dosing subjects in the remainder of the cohort will be at the discretion of the investigator (in consultation with the sponsor, if required) i.e. this could be increased or decreased as appropriate.

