- d. All female subjects.
- e. Residential Periods: Discharge from clinic after completion of Day 4 and Day 11 assessments as applicable.
- f. Full physical examination at screening, Day 17 and EDV. Symptom directed examination; if required at any other visits or times at the discretion of the investigator.
- g. Clinical safety laboratory samples (clinical chemistry, haematology and urinalysis) must be performed within 7 days of Day 1; if this interval is exceeded, sampling must be repeated. Samples for clinical chemistry will be obtained following a fast of at least 8 hours (water permitted).
- h. 24 hours post 0-hour dose Day 1 and prior to Day 2, 0-hour dose administration.
- i. Prior to 0-hour dosing.
- j. 24 hours post the 0-hour dose on Day 10.
- k. Performed in triplicate. For assessment of time windows, the time of the first ECG of the triplicate will be used.
- I. Performed at 2 and 4 hours post 0-hour dose.
- m. Pre-dose (0-hour) and post 0-hour dose at 2 and 4 hours.
- n. Systolic and diastolic blood pressure, pulse rate and respiratory rate.
- o. Performed at 0.5, 2, 4, 8 and 12 hours post 0-hour dose. If dosing is BID, the 12-hour assessment will be performed before the evening (i.e. 12-hour) dose.

- p. Pre-dose (0-hour) and post 0-hour dose at 0.5, 2, 4, 8 and 12 hours.
- q. Pre- and post-bronchodilator (salbutamol) reversibility testing at screening. At all other visits and time-points, spirometry may be performed pre- or post-bronchodilator; i.e. there are no requirements for bronchodilator restrictions after the screening visit.
- r. Performed at 0.5, 2, 4 and 8 hours post 0-hour dose.
- s. Pre-dose (0-hour) and post 0-hour dose at 0.5, 2, 4 and 8 hours.
- t. On Days 4 to 9 the subjects will be required to attend the unit for the evening for their 12-hour dose (i.e. return in the evening on Day 4 and attend twice daily on Days 5 to 9) if dosing is BID.
- u. **PK blood samples**: at 1.5, 2, 3, 4 and 12 hours post 0-hour dose. If dosing is BID, the 12-hour sample will be collected before the evening (i.e. 12-hour) dose.
- v. **PK blood sample:** at 24 hours post 0-hour dose Day 1 and prior to Day 2, 0-hour dose administration. If dosing is BID, the 24 hour sample can be taken anytime pre-dose on Day 2.
- w. PK blood samples: Pre-dose (0 hour) and post 0-hour dose at 1.5, 2, 3, 4 and 12 hours.
- x. Induced Sputum Samples for PK assessments: Pre-dose (0 hour) and post 0-hour dose at 3 hours and 6 hours.

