4.1.2. Part 2 (MAD)

Part 2 is a multiple ascending dose (MAD) study to assess the safety, tolerability and PK of multiple doses of ZP-059 in 3 cohorts of male and female subjects with a physician confirmed documented diagnosis of mild stable asthma. Each cohort will comprise 6 subjects (planned total of 18 subjects). An evaluable subject for Part 2 (MAD) of the study is defined as a subject who has received 10 days of dosing with ZP-059 and has sufficient data for evaluation of the objectives of the study.

Up to 2 optional additional cohorts of 6 subjects (Cohort 4 and Cohort 5) may be enrolled in Part 2 if it is deemed appropriate to repeat a dose level, assess an additional dose level or assess a different dosing regimen (), however, the dose will not exceed the highest dose studied in Part 1 (Section 6.6.2). If a selected dose does not provide the required data to meet the objectives of the study, a previously tested dose may be used in a subsequent cohort. However, if the dose level met the dose escalation or study stopping criteria, neither that dose level nor a higher dose will be repeated.

In each cohort, subjects will receive inhaled doses either once daily (QD) for 10 days or twice daily (BID) for 9 days and once in the morning of Day 10, as determined by the Sponsor based on data obtained in previous Part 1. In the event of QD dosing eligible subjects will receive QD doses of ZP-059 (at Hour 0) on Days 1 to 10. In the event of BID dosing, ZP-059 will be administered at Hours 0 and 12 on Days 1 to 9 and once in the morning of Day 10 (i.e. 19 doses in total). Subjects will be required to fast (water permitted) for at least 1 hour prior to each dose and 1 hour post each dose; in the event

of BID dosing this will be for both the 0 hour and the 12 hour doses. Following the first dose, subsequent doses will be administered within +/- 1 hour of the scheduled dosing time. If any of the additional cohorts (i.e. Cohorts 4 and 5) are required, subjects will receive either QD or BID doses, as may be appropriate.

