9.4.1. General considerations

For study parts 1 and 2, background and demographic characteristics and safety data will be summarised by ZP-059 dose and overall doses. PK data will be summarised by ZP-059 dose only.

For study part 3, background and demographic characteristics will be summarised by treatment sequence and overall. Safety and PK data will be summarised by treatment: Test (ZP-059) or Reference (oral voriconazole).

Full details of the statistical analyses will be provided in a separate statistical analysis plan (SAP), which will be finalised before database lock.

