#### 7.12.3 Dose proportionality

Dose proportionality of ZP-059 will be assessed by fitting a power model as follows:

$$log_{10}(y) = \alpha + \beta \ log_{10}(dose)$$

Where  $\alpha$  represents the random subject effects for intercept and dose. A value of 1 for  $\beta$  indicates perfect dose proportionality. Therefore, the estimate of  $\beta$  together with the corresponding 90% confidence interval (CI) will be used to quantify dose proportionality. The increase in concentration over the dose range will be estimated by the ratio of the expected concentration with the highest dose to that of the lowest dose. This will be derived by back-transforming the difference on the log10 scale between the two doses and will be accompanied by its associated 90% confidence interval. If the exposure is dose proportional there should be a fold increase equal to the ratio of highest: lowest dose across the dose range.

If it isn't possible to fit random subject slopes a common fixed effect slope will be fitted.

Dose proportionality will be assessed for each of the following PK endpoints for voriconazole and n-oxide voriconazole separately:

- Cmax
- AUC0-t, where t is 12 hours for Part 1, 24 hours for Part 2 and 96 hours for Part 3.
- AUC0-inf

These will be performed separately for Part 1 and Part 2 at Day 1 and Day 10. This analysis will be performed if 3 or more dose levels are used for the Part.

Dose proportionality will also be assessed using an analysis of variance (ANOVA) method. A mixed effects model will be fitted with fixed effects for dose and random effects for subject. The difference between the dose levels will be presented along with a 90% confidence interval and p-value.

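### Part 2 summaries and exposure models carry no QD/BID factor, so if any cohort is BID its Day 1 AUC0-24 spans two doses, and if regimens differ between cohorts dose is confounded with regimen

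*SAP*

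**What the plan says.** **Regimen.** Protocol 1.1 (Part 2): "In each cohort, subjects will receive inhaled doses either once daily (QD) for 10 days or twice daily (BID) for 9 days", followed by one morning dose on Day 10. Protocol 4.1.2 repeats this and allows optional Cohorts 4 and 5 to "repeat a dose level, assess an additional dose level or assess a different dosing regimen".

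**Grouping.** SAP 7.5.1: "safety and PK data will be summarised by ZP-059 dose only". It adds "Dose groups will be presented in the following order using these labels", and the labels that follow give mg only. Protocol 9.4.1 agrees: "PK data will be summarised by ZP-059 dose only".

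**Models.** SAP 7.12.3: "Dose proportionality of ZP-059 will be assessed by fitting a power model as follows". The only predictor is log10(dose), and the supplementary ANOVA has dose and subject only. The modelled endpoints are Cmax, AUC0-inf and AUC0-t, "where t is 12 hours for Part 1, 24 hours for Part 2 and 96 hours for Part 3". SAP 7.12.4 compares Part 3 with Part 2 using population group and sex. It does not say which Part 2 day is used.

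**Sampling.** Protocol 1.2.2 schedules Part 2 Day 1 serum samples at 1.5, 2, 3, 4 and 12 h. Under BID the 12 h sample precedes the evening dose. For the next sample: "If dosing is BID, the 24 hour sample can be taken anytime pre-dose on Day 2".

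**Caveats.** SAP 3.2.2 calls 24 h nominal for Part 2 and says that the last time point may depend on regimen. It warns about Day 1 AUC0-inf under BID and lists AUCtau on Days 1 and 10.

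**The concern.** Regimen is chosen cohort by cohort, yet nothing in the planned grouping or models records it. Three consequences follow, each under its own condition.

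- **If any cohort is BID**, its Day 1 AUC0-24 is a two-dose quantity measured with one trough sample after the second dose. It is not comparable with a QD cohort or with single-dose Part 3 data, although Protocol 3.2.2 intends the Part 3/Part 2 comparison to be like for like.
- **If regimens differ between cohorts**, the dose models attribute a regimen effect to dose, which could be reported as departure from proportionality.
- **If one mg level is given under both regimens**, one safety or PK column would pool subjects who had 10 doses with subjects who had 19. SAP 7.10 lists individual exposure but plans no table that would show this.

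**Working it through.** **1. The plan's own figure.** BID doses per subject: 2 × 9 + 1 = 19, as Protocol 4.1.2 states. QD gives 10.

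**2. Samples around the second Day 1 dose (Protocol 1.2.2).** Strictly between 12 h and 24 h: none scheduled. After the evening dose and before the Day 2 dose: one, nominally at 24 h.

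**3. Assumptions not in the documents.** One compartment, first-order absorption, linear kinetics, half-life 4 to 12 h, ka 2 to 6 per h, linear trapezoid, Day 2 sample at exactly 24 h. For a unit dose and volume, C(t) = ka/(ka − ke) × (e^(−ke·t) − e^(−ka·t)), with ke = ln 2 / half-life. BID adds C(t − 12) after 12 h.

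**4. One case by hand** (half-life 6 h, ka 3 per h). ke = 0.1155 and ka/(ka − ke) = 1.040.
- C at 12 h = 1.040 × 0.25 = 0.260. C at 24 h = 1.040 × 0.0625 + 0.260 = 0.325.
- Trapezoid for 12 to 24 h: 12 × (0.260 + 0.325)/2 = 3.51.
- True area for 12 to 24 h: first-dose remainder 0.260 × 0.75/0.1155 = 1.69, plus second dose 1.040 × (0.75/0.1155 − 1/3) = 6.40, total 8.09.
- The scheduled samples miss 57% of that interval.

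**5. Full range.** The table is at ka = 4 per h, and the last row covers ka 2 to 6 per h. Ratios are BID/QD at the same nominal dose.

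| Half-life (h) | Day 1 BID AUC0-24, sampled/true | Day 1 ratio, sampled | Day 1 ratio, true | Day 10 AUC0-24 ratio |
|---|---|---|---|---|
| 4 | 0.61 | 1.14 | 1.88 | 1.13 |
| 6 | 0.66 | 1.19 | 1.79 | 1.26 |
| 8 | 0.70 | 1.22 | 1.73 | 1.36 |
| 12 | 0.73 | 1.24 | 1.66 | 1.51 |
| Range | 0.60–0.75 | 1.14–1.24 | 1.65–1.89 | 1.13–1.51 |

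Wider assumptions (half-life 3 to 24 h, ka 1 or 3 per h) give a sampled Day 1 ratio of 1.09 to 1.26 and a true ratio of 1.56 to 1.94.

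**6. Day 10 check.** A BID cohort gets one dose on Day 10 but carries more residual drug. With very fast absorption the ratio is 1 + 2^(−12/half-life): 1.125 at 4 h and 1.50 at 12 h. Cmax moves by the same factor. Regimen-specific AUCtau does not: at steady state, AUC0-12 under BID and AUC0-24 under QD both equal the single-dose AUC0-inf.

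**7. Effect on the slope.** For three doubling doses with only the top one BID, the least-squares slope shifts by ln(R)/(2 ln 2). On Day 10, R = 1.13 gives 0.122/1.386 = +0.09, and R = 1.51 gives 0.412/1.386 = +0.30. If only the lowest dose is BID, the sign reverses.

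**8. Part 3/Part 2 ratio at equal dose, Day 1 AUC0-24, Part 2 BID.** As sampled: 1/1.24 = 0.81 to 1/1.14 = 0.88. With full sampling: 1/1.89 = 0.53 to 1/1.65 = 0.61. Neither departure from 1 reflects a population difference.

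**The case against.** - **Mixing is possible, not planned.** A reader might infer that QD and BID cohorts will be pooled. The documents do not say so. SAP 3.3 ties dose and frequency to the review after Part 1 Cohort 2, so one regimen throughout is plausible. Columns pool only if one mg level has both regimens, and models confound only if cohorts differ. This stands and sets the conditions above. It does not help the Day 1 AUC0-24 of a BID cohort, which spans two doses even if every cohort is BID.
- **There is a sample after the evening dose.** One might read the schedule as having none. The Day 2 pre-dose sample exists; the absorption and peak phase is what goes unsampled.
- **The word 'only' should not be over-read.** In SAP 7.5.1 it contrasts with summaries by dose group and overall, so it mainly means no overall column. The point rests on the mg-only labels and the absent regimen term. The table shells are a separate document and might show regimen.
- **The SAP is not silent.** SAP 3.2.2 allows the last time point to depend on regimen and derives AUCtau. But it gives no rule, 7.12.3 restates 24 h for Part 2, and AUCtau is not a modelled endpoint.
- **Stakes are limited.** The analyses are unpowered and carry no formal hypothesis test, and SAP section 6 says no outputs from these analyses feed the safety reviews. This stands: the risk is misreported pharmacokinetics and unclear safety columns, not wrong escalation decisions.

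**Conclusion.** The point holds conditionally. The SAP has no regimen factor in its Part 2 summaries, power model, dose ANOVA or Part 3/Part 2 comparison, and does not define 'dose', although each cohort may be QD or BID.

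If any cohort is BID, following 7.12.3 as written gives a Day 1 AUC0-24 that is 60 to 75% of the true value and not comparable with QD or Part 3 data. If regimens differ between cohorts, the Day 10 slope could shift by +0.09 to +0.30 in the layout shown. The directions follow from the dosing and sampling times. The sizes rest on assumed half-life, ka and linear kinetics, and on one particular layout of doses.

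Day 1 Cmax needs no change under these assumptions: the 24 h trough is 0.18 to 0.86 of the first-dose peak, so the observed maximum is already that of the first dose. Nothing here bears on which regimen should be given.

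**What to change.** 1. **SAP 7.5.1:** label and group Part 2 by dose and regimen (for example, XX mg QD and XX mg BID), and carry this into the shells.
2. **SAP 7.12.3:** define 'dose' as dose per administration.
3. **Day 1, whenever any Part 2 cohort is BID:** use AUC0-12 for all Part 2 cohorts in the dose-proportionality model and in the Part 3/Part 2 comparison, with Part 3 derived over the same window. Every cohort can supply it, because the 12 h sample precedes any second dose. Do not model or compare AUC0-24 for BID cohorts.
4. **Day 10:** use AUCtau (tau 12 h for BID, 24 h for QD) and Cmax,ss, within one regimen or with a regimen term. Cmax,ss needs this separation even under linear kinetics.
5. **SAP section 2:** record the change, because Protocol 9.4.4 names AUC0-t at 24 h as a Part 2 endpoint.

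**Cost.** SAP text, shells and one entry in section 2; no new data. The real downside is fewer dose levels per model. With three cohorts of mixed regimen, a within-regimen fit falls below the SAP's condition of three dose levels. A regimen term for a single BID cohort leaves the slope resting on two doses. The SAP should say that the results are then reported descriptively.
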